7.2 SUBJECT DISPOSITION

There will be a clear accounting of all subjects who are enrolled onto dose optimization. The following will be summarized by treatment sequence group for all enrolled subjects:

- The number of subjects who are enrolled onto dose optimization
- The number of subjects who receive study medication
- The number of subjects in Safety population
- The number of subjects who are randomized into double-blind
- The number of subjects in FAS population
- The number of subjects in Completers population
- The number of subjects who complete the study
- The number of subjects who discontinued the study and reason for discontinuation

The reasons for all study discontinuations will be summarized by treatment sequence, by treatment arm and study period, and will also be provided as a by-subject listing. The number and percentage of randomized subjects in each of the three efficacy study populations will be summarized for all subjects combined and for each treatment sequence.

7.3 PROTOCOL DEVIATIONS AND VIOLATIONS

All major protocol deviations or violations (PDVs) for each subject will be reviewed on blinded data prior to database lock to evaluate whether the subject has been protocol compliant. Major PDVs will be assessed as to whether or not they have a significant impact on the assessment of efficacy.

Major protocol violations will include, but are not limited to the following:

- Dosing non-compliance
- Deviation from visit window during the double-blind phase
- Non-permitted concomitant medications
- Violation of Inclusion/Exclusion Criteria

The number of subjects with each type of major PDV will be tabulated by category and by deviation type for all subjects in the SP population. A listing of all PDVs including deviation date, deviation type, deviation description and any relevant comments will be generated.

7.4 TREATMENTS

7.4.1 Extent of Study Drug Exposure

The duration (days) of study drug dosing will be determined as follows for each subject and summarized by treatment arm and overall for both SP and Completers populations:

Duration of study drug dosing overall for the double blind period (days) = date of last dose – date of first dose of double blind treatment + 1.

The date of first dose of double blind treatment will be Visit 5 + 1 day according to the protocol. Duration of study drug dosing per visit (days) = date of last dose at that visit – previous visit date The percent compliance with study medication will be calculated at each visit and for the overall double-blind Treatment Period.

Percent compliance = $\{[(\text{Total number of patches dispensed}) - (\text{Total number of patches returned unused})]/ \text{number of days in the interval}\} * 100\%$

The duration of study drug dosing and percent compliance will be summarized by visit and overall for both Safety and Completers populations.

Treatment dose at each visit during the dose-optimization phase will be summarized for the Safety population. A summary table for treatment dose for each treatment and period for the double-blind phase will be also presented.

All dosing and compliance data also will be provided as data listings.

7.4.2 Concomitant Medications

All prior and concomitant medications recorded in the electronic case report form (eCRF) will be coded to generic term and all matching Anatomic Therapeutic Classification (ATC) codes using the current version of WHO Drug. Summaries will be prepared using the coded generic term.

The number and percentage of subjects who had prior medications will be provided by preferred drug name for the SP population. The numbers and percentages of subjects who had concomitant medications during the Dose-Optimization Period and during the double-blind Treatment Period will be presented separately for the SP population.

All prior and concomitant medications recorded in the eCRF will be listed.

7.5 DEMOGRAPHIC AND BASELINE CHARACTERISTICS

Demographics and baseline characteristic data will be summarized by treatment arm for both the SP population and FAS. Demographic and baseline characteristics include, but are not limited to, age, age group, gender, race, ethnicity, weight, height, BMI, ADHD subtype, ADHD-RS-IV total (continuous and group) and subscale scores at baseline. Age will be calculated based on the date of informed consent, and the weight and height measurements will be those measured at screening. A category of 'Multiple' will be defined for race to summarize those subjects selecting more than one; all selections will be listed.

7.6 DERMAL EVALUATIONS

Summaries of dermal evaluations will be based on the SP population. Summary statistics will be presented separately for the SP population on all subjects combined during the Dose-Optimization Period and by treatment arm during the double-blind Treatment Period.

No statistical analyses will be performed for the dermal evaluation data.

7.6.1.1 ADHESIONS

The source data are the adhesion scores of the patches. Data from the in-clinic assessments will be summarized for each treatment arm.

- Frequency table showing the number of patches with each adhesion score at each evaluation time point.
- The number of patches that detached will be summarized.
- For detached patches, the duration of patch wear before patch detachment will be summarized (time of patch detachment will be subtracted from time of application).

7.6.1.2 IRRITATION

The source data will be the actual irritation scores recorded following visual evaluation of the application sites. If a patch is removed due to irritation, Last Observation carried Forward (LOCF) will be applied for all remaining time points. LOCF is defined as the highest irritation score observed prior to discontinuation of the patch due to irritation.

The letter grades will be converted to numerical equivalents in the following way: N (none)=0, A=0, B=1, C=2, and F, G, and H=3. For each subject, a combined score will be derived by adding the numerical grade and the numerical equivalent of the letter grade at each evaluation time point (e.g., 2C=2+2=4). Missing values for ‘Other Effects’ when the applicable numerical value is “0” will be calculated as a score of “N” with a numerical value of “0”. Analyses for this data will be identified as combined scores.

The following data from the in-clinic assessments will be provided for each treatment arm:

- Frequency table with each combined “Dermal Response” and “Other Effect” score using worst case for all subjects.
- Frequency table with each combined “Dermal Response” and “Other Effect” score using worst case for subjects who discontinued due to irritation.
- Summary of number of patches that were removed due to irritation and number of patches that were removed due to irritation split by irritation combined score assessed at 30 minutes after detachment/removal

All irritation scores will be listed, including those captured in the dermal evaluation diary.

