Dermal Evaluations	
Dermal evaluations will be completed at home and during the clinic visits as follows:
 
 
Application site will be evaluated by Parents/Caregivers/Subjects for local skin irritation, discomfort, adhesion, and adhesive residue daily.
 
Adhesion and discomfort will be evaluated by site personnel at 1 and 2 hours after d-ATS patch application on Visit 5 (Day 35) and at 1, 2, 4, 8, and 9 (prior to removal) hours after d-ATS patch application on Visit 6 (Day 42) and Visit 7 (Day 49).
 
For discomfort scores greater than 0, discomfort will also be evaluated at 1 and 2 hours hours after d-ATS patch application on Visit 5 (Day 35) and at 1, 2, 4, 8, and 9 hours on) Visit 6 (Day 42), and Visit 7 (Day 49) using the 10-point Wong-Baker Faces or Visual Analog Scale (age dependent). A <math>\pm</math> 15 minute window is permissible.
 
Site personnel will evaluate skin irritation 24 hours after removal of the previous day's patch on Visit 6 (Day 42) and Visit 7 (Day 49).
 
Site personnel will evaluate skin irritation prior to patch application and at 30 minutes, 1 and 3 hours after patch removal on Visit 6 (Day 42) and Visit 7 (Day 49).
 
Immediately following the removal of the patch on Day Visit 6 (Day 42) and Visit 7 (Day 49) or early termination the amount of adhesive remaining at the application site will be examined and graded.
 

Outcome Measures:	
Primary Efficacy Measure: The primary efficacy measure is the mean SKAMP total score. Multiple SKAMP

Amendment 4: Version 5.0 May-08-2013

Amendment 3: Version 4.0 December-11-2012

Amendment 2: Version 3.0 October-31-2012

Amendment 1: Version 2.0 August-02-2012

Final Protocol May-25-2012

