#### 5.3.4.2 Visit 1 (Day 7), Visit 2 (Day 14), Visit 3 (Day 21), Visit 4 (Day 28) and Visit 5 (Day 35) – Clinic Days

Subjects will return to the clinic for evaluations on Day 7  $\pm$ 3 days, Day 14  $\pm$ 3 days and Day 21  $\pm$ 3 days, Day 28  $\pm$ 3 days and Day 35  $\pm$ 2 days. There must be at least 4 days in between clinic visits). The following evaluations will be performed during each clinic visit:

1. Record any AEs or concomitant therapy since previous visit.

Amendment 4: Version 5.0 May-08-2013

Amendment 3: Version 4.0 December-11-2012

Amendment 2: Version 3.0 October-31-2012

Amendment 1: Version 2.0 August-02-2012

Final Protocol May-25-2012

2. Perform drug accountability and collect all used and unused patches.
3. Review the daily dosing and irritation diaries for compliance.
4. Obtain vital signs (sitting BP, HR, RR, oral body temperature).
5. Record weight.
6. Perform a 12-lead electrocardiogram (ECG) on Day 35.
7. Perform urine pregnancy testing on all female subjects of child-bearing potential.
8. Obtain ADHD-RS-IV score (home version).
9. Perform 1 PERMP (for practice on days 7, 14, 21, and 28) at demonstrated level.
10. Half-day classroom with SKAMP and PERMP (Visit 5, Day 35) pre-dose and 1 and 2 hours post-dose (SKAMP and PERMP rating periods will be 20 minutes in duration).
11. Patch application in clinic (Day 35 only) by subject/parent/caregiver/site personnel
12. Adhesion and discomfort will be evaluated by site personnel after d-ATS patch application at 1 hour and 2 hours/ immediately prior to leaving the clinic on Visit 5 (Day 35).
13. For discomfort scores greater than 0, discomfort will also be evaluated at 1 and 2 hours after d-ATS patch application on Visit 5 (Day 35) using the 10-point Wong-Baker Faces or Visual Analog Scale (age dependent). A  $\pm$  15 minute window is permissible.
14. Site personnel will evaluate skin irritation of the previous day's patch near subject dismissal on Visit 5 (approximately 19 hours after removal of the patch).
15. Administration of the C-SSRS (Children's Since Last Visit version) by a trained staff member.
16. Perform CGI-I.
17. Based on the ADHD-RS-IV score, CGI-I score and side effect profile, adjust the subject's dose to the next available dose (except Visit 4, which can only be a dose reduction and Visit 5 (randomization at optimal dose))

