### **5.3.6 *Early Termination***

If the subject is discontinued early (prior to Day 49), the following procedures will be performed:

1. Record any AEs or concomitant therapy since previous visit.
2. Perform drug accountability and collect all used and unused patches.
3. Obtain vital signs (sitting BP, HR, RR, oral body temperature).
4. Obtain weight.
5. Collect blood and urine for clinical laboratory assessments
  - Complete Blood Count (including differential and platelet count)
  - Blood Chemistry
  - Urinalysis
6. Perform a 12-lead electrocardiogram (ECG) prior to discharge.
7. Perform complete physical examination
8. Perform urine pregnancy testing on all female subjects of child-bearing potential.

Amendment 4: Version 5.0 May-08-2013

Amendment 3: Version 4.0 December-11-2012

Amendment 2: Version 3.0 October-31-2012

Amendment 1: Version 2.0 August-02-2012

Final Protocol May-25-2012

9. Obtain ADHD-RS-IV score.
10. Perform CGI-I.
11. Administration of the C-SSRS (Children's Since Last Visit version) by a trained staff member.
12. Dismiss from clinic.
13. Contact IVRS/IWRS to early discontinue the subject in the system.

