## 6.16 Dermal Evaluations

A trained individual will evaluate the d-ATS application site for adhesion of the patch to the skin and for any discomfort or irritation caused by it. The evaluator will observe the skin directly under the clear d-ATS, without removing the system, and interview the subject. Post-removal, the evaluator will assess the application site and the surrounding area for irritation and adhesive residue. Dermal evaluations must be completed in accordance with the instructions listed below.

In order to ensure reliability between successive ratings, a dedicated evaluator should follow each subject through the completion of the study. If this is not possible, then every effort must be made to limit the number of evaluators to two. *Signs and/or symptoms of discomfort or irritation related to the patch should NOT be recorded as AEs, unless (i) they occur at a site different from the application site; (ii) if the subject or patch application site is discontinued prematurely from the study due to discomfort or irritation at the patch site; (iii) the symptoms of discomfort or irritation are so severe that in the investigator's judgment it should be recorded as an AE; (iv) the subject requires a concomitant therapy to treat discomfort or irritation. If discomfort or irritation is recorded as an AE then the AE will be followed to resolution or up to 30 days following patch removal, whichever comes first.*

Spontaneous complaints of irritation or discomfort at the patch application site at times that are unscheduled will be also recorded. Spontaneous reports might include but are not limited to the following: initial complaint irritation or discomfort, exacerbation of an existing irritation or discomfort. The time elapsed between the unscheduled evaluation and d-ATS application must be recorded. At times when the laboratory classroom is scheduled on the same hour as a dermal evaluation, the dermal evaluation may take place up to 10 minutes prior to the start of the classroom.

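### The dermal tables use only site scores from Visit 5 onwards and leave the daily home diary untabulated, so sub-AE irritation and discomfort on home days, home detachments and home residue reach no planned summary

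*SAP*

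**What the plan says.** Skin irritation, discomfort, adhesion and residue are a secondary objective in both documents. SAP 7.6 says dermal summaries will cover the Safety population, all subjects combined, in dose optimisation, and will be by treatment in the double-blind period.

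The subsections narrow this:
- **Adhesion (SAP 7.6.1.1):** "Data from the in-clinic assessments will be summarized for each treatment arm".
- **Irritation (SAP 7.6.1.2):** "The following data from the in-clinic assessments will be provided for each treatment arm". One of the tables that follow gives combined scores "using worst case for subjects who discontinued due to irritation". On the diary: "All irritation scores will be listed, including those captured in the dermal evaluation diary".
- **Discomfort and residue (SAP 7.6.1.3 and 7.6.1.4):** scores recorded in clinic are summarised, and diary entries are listed.

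At home, protocol 6.16.1 to 6.16.4 collect four things every day: whether the patch is attached (with the time if it fell off), discomfort yes or no, irritation yes or no with a description, and a residue grade.

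At the site, protocol 5.3.4.2 lists no dermal scoring at Visits 1 to 4. Its one irritation reading is of the previous day's patch, "near subject dismissal on Visit 5 (approximately 19 hours after removal of the patch"). Protocol 5.3.5.3 schedules full scoring at Visits 6 and 7.

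For early leavers, protocol 5.3.6 begins "If the subject is discontinued early (prior to Day 49), the following procedures will be performed" and lists 13 items, none of them dermal. The synopsis, under Dermal Evaluations, nevertheless says that on Days 42 and 49 "or early termination the amount of adhesive remaining at the application site will be examined and graded".

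Protocol 6.16 sets the adverse event rule: "Signs and/or symptoms of discomfort or irritation related to the patch should NOT be recorded as AEs, unless" one of four conditions applies. These are a reaction away from the application site, premature discontinuation, severity in the investigator's judgement, or need for concomitant therapy.

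**The concern.** Five weeks of open-label titration, with patch size rising, are where most d-ATS exposure occurs. Protocol 6.16 deliberately keeps ordinary application-site reactions out of the adverse event data, so for those reactions the dermal tables are the only planned summary. If those tables draw only on site scores from Visit 5 onwards, they describe children who tolerated the patch well enough to get there. The table for subjects who discontinued due to irritation has no scheduled score for anyone who left before Visit 5. What is at stake is whether the trial can report its dermal objective for the treated population, using data that families are already asked to record every day.

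**Working it through.** The plan states no figure for this point, so there is nothing to reproduce. The check is a comparison of texts and a count of scheduled assessments.

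**1. SAP against protocol.** Protocol 8.3.1 (adhesion) and 8.3.4 (residue) already say in-clinic, so for those two the SAP matches. Protocol 8.3.2 (irritation) and 8.3.3 (discomfort) carry no such limit; the SAP adds one, while SAP 1.1 reports no changes from the protocol.

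**2. Source of scores for early leavers.** SAP section 7 maps early-termination assessments to the next scheduled visit. Because protocol 5.3.6 lists no dermal score, there is no scheduled score to map. Home irritation entries are yes or no, so they cannot supply the combined score either.

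**3. Scheduled site irritation readings** (protocol 5.3.4.2 and 5.3.5.3).
- Day 35: 1 reading.
- Days 42 and 49: 5 each (pre-application; 30 minutes, 1 hour and 3 hours after removal; previous day's patch).
- Total: 1 + 5 + 5 = 11 readings, on 3 of 49 treatment days (3/49 = 6.1%).
- In dose optimisation: 1 of 35 days (2.9%), and none of Visits 1 to 4.

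**4. Share of d-ATS patches assessed by site staff,** for a child who completes on the nominal schedule. Patches worn: 35 (Days 1 to 35) + 7 (one double-blind week) = 42.
- Adhesion: the Day 35 patch (first 2 of 9 hours only) and the Day 42 or 49 patch, 2/42 = 4.8%. Discomfort follows the same timetable.
- Residue: the Day 42 or 49 patch, 1/42 = 2.4%.
- Irritation: the Day 34 patch, the Day 41 or 48 patch and the Day 42 or 49 patch, 3/42 = 7.1%. Counting the pre-application check as a further patch gives 4/42 = 9.5%.

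**5. Illustration of the denominator effect.** The documents give neither the number entering dose optimisation nor a rate of withdrawal for irritation. Assume 90 children have site scores, none of them severe, and k others left earlier because of irritation. The score table shows 0/90. The share of all exposed children who left for irritation is k/(90 + k):

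| k | k/(90 + k) |
|---|---|
| 1 | 1.1% |
| 3 | 3.2% |
| 5 | 5.3% |
| 10 | 10.0% |
| 15 | 14.3% |

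These values show the mechanism only; they are not an estimate for this trial.

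**The case against.** The strongest reply is that the worst reactions are already covered. Under protocol 6.16, irritation or discomfort that causes withdrawal, is judged severe or needs treatment must be recorded as an adverse event. It then receives a severity grade (protocol 6.17.1). SAP 7.7.1 tabulates such events by period and dose at onset, including tables by intensity and of events leading to discontinuation. SAP 7.2 also tabulates reasons for discontinuation by period. This stands. A reader might infer that children who leave because of irritation drop out of every summary; the documents do not support that. They are missing from the dermal-scale tables only. The route does not cover reactions below the threshold, nor detachment or residue as such, and a three-point severity grade cannot fill a combined-score table.

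Second, a reader might take the planned split by score 30 minutes after removal to be unworkable for patches removed at home. The in-clinic lead-in in SAP 7.6.1.2 already governs that table, so little is wrong there.

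Third, concentrating graded scoring on classroom days is a legitimate design choice, and d-ATS and placebo are compared on matching days. Yes/no diary answers also cannot be pooled with the graded scales. Both points are fair. They argue for separate diary tables, not for none.

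Fourth, the row labels of Appendix 1 cannot be read in the available text, and the SAP's table shells are not in it. Site checks at Visits 1 to 4 or at early termination could be marked in the schedule. If so, the schedule conflicts with protocol 5.3.4.2 or 5.3.6, and reconciliation is still needed.

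**Conclusion.** The point holds as one of reporting and consistency. The dermal-scale tables describe children who reached Visit 5 or later. The score table for irritation discontinuers has no scheduled source before then. The SAP narrows the protocol for irritation and discomfort without saying so. Irritation and discomfort below the adverse event threshold on home days, home detachments and home residue scores reach no planned summary. On each dermal scale, over 90% of a completing child's d-ATS patches have no site assessment; this assumes nominal visit days and relies on the procedure text and SAP body.

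Two further inferences are not supported. One is that irritation is understated by a known amount: the fraction of patches graded measures sampling, not bias, and no withdrawal or irritation rate is given. The other is a total of 90 × 42 = 3,780 patch-days, which would require all 90 randomised children to complete, whereas the plan expects 74.

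**What to change.** **SAP 7.6.** Add descriptive tables of the diary for the Safety population, by week and dose worn in dose optimisation and by treatment in the double-blind period. Give the number and percentage of children and of patch-days with any irritation, any discomfort, complete detachment and each residue score. Label them as home-rated, and as open-label in dose optimisation. In every dermal table show the number with site grades beside the number exposed, and cross-refer to the application-site TEAE and discontinuation tables. Record in SAP 1.1 that the irritation and discomfort score tables are limited to clinic data.

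**Protocol 5.3.6.** Reconcile it with the synopsis and SAP 7.6.1.2. Add the existing Table 3 and Table 4 irritation scores at early termination, where a complete physical examination that includes skin already takes place (protocol 6.8). Add the Table 5 residue score only when a patch is removed at that visit, because protocol 6.16.4 grades residue immediately after removal. Check Appendix 1 against both.

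**Cost.** The SAP part is a few tables from data already collected, and it can go into the final SAP before database lock. Its limitation is that the entries are not staff-rated. The early-termination item needs a small protocol amendment with IRB approval (protocol 10.4) and helps only children who leave after it takes effect.

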7.6.1.3 DISCOMFORT

The source data will be the discomfort scores of the patches. A summary of Discomfort Scores recorded in clinic will present the discomfort scores and a summary of Description of Discomfort with the number and percent of subjects by each treatment and time point.

The Wong Baker Faces Scores (WBS) and Visual Analog Scale (VAS) scores will be presented separately and combined, by treatment for each timepoint. For the separate analyses the WBS and VAS will each be summarized by presenting mean, SD, median, minimum, maximum and IQR. For the combined analyses the numerical value of the scales will be taken and used to present combined continuous summary statistics. Additionally the WBS and VAS scores will be converted to the Numeric Rating Scale (NRS-11) and presented in combination under the Pain

Level with the number and percentage of subjects falling into each category. Subjects that do not provide a WBS or VAS score due to the discomfort assessment being 0 (no discomfort) will be included in the Rating level 0 and Pain Level of No Pain.

Numeric Rating Scale (NRS-11):	
Rating	Pain Level
0	No Pain
1-3	Mild Pain
4-6	Moderate Pain
7-10	Severe Pain

All discomfort scores, including the WBS and VAS scores, will be listed, including those captured in the dermal evaluation diary.

